22. BONE MARROW ANALYSIS

A bone marrow histological evaluation is performed to all patients recruited that provided the specific consent in **Part B** in order to assess the presence of age adjusted normocellularity and/or trilinear hyperplasia as requested by the “new” ELN response criteria (i.e. the revised ELN response criteria) [2].

This examination is performed in the local laboratory of each site. The results of this test are transcribed into the electronic CRF and the original signed and dated laboratory print-out/tracings, including the assessment of the presence of age adjusted normocellularity and/or trilinear hyperplasia, is monitored and stored at the study site.

Notably, in case the patient performs the bone marrow histological evaluation as requested by the “new” ELN criteria (i.e. the revised ELN response criteria) [2] – i.e. bone marrow evolution including the assessment of the presence of age adjusted normocellularity and/or trilinear hyperplasia - 1 month before the study start (i.e. the signature of the “primary” ICF), this examination has not to be repeated for this Study in order to limit the discomfort for the patient. In any case, the results of this test are transcribed into the electronic CRF and the original signed and dated laboratory print-out/tracings, including the assessment of the presence of age adjusted normocellularity and/or trilinear hyperplasia, is monitored and stored at the study site.

In case the patient drops-out the Study during the first 3 Cycles (i.e. before the C3D28), this evaluation has not to be performed at EOS visit.

Finally, in case the patient refused to provide this written consent to perform the bone marrow evaluation, this patient can still be recruited in Part B. However, this patient will not be counted to assess the related exploratory endpoints (i.e. overall response rate of Givinostat at the MTD after 6 cycles according to the revised ELN response criteria [2], and the evaluation of the effect of Givinostat on each single response parameter according to the revised ELN response criteria [2]).

The following information will be provided for the bone marrow histological evaluation:

- Number (n) and percentage (%) of patient with marrow histological evaluation;
- Number (n) and percentage (%) of presence of age-adjusted normocellularity;
- Number (n) and percentage (%) of trilinear hyperplasia absence;
- Number (n) and percentage (%) of grade >1 reticulin fibrosis absence;
- Listing of reason of not performed evaluation.

Document: PPD

Author: PPD

Version Number:

V2.2

Version Date:

21 March 2018

Template No: CS_TP_BS016 – Revision 3

Reference: CS_WI_BS005

Effective Date: 01May2012

Copyright © 2012 Quintiles Transnational Corp. All rights reserved.

The contents of this document are confidential and proprietary to Quintiles Transnational Corp. Unauthorized use, disclosure or reproduction is strictly prohibited.

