The contents of this document are confidential and proprietary to Quintiles Transnational Corp. Unauthorized use, disclosure or reproduction is strictly prohibited.

- **Complete remission:**
 1. *Durable* resolution of disease-related signs including palpable hepato-splenomegaly improvement, and *large symptoms improvement*, **and**
 2. *Durable* peripheral blood count remission, defined as HCT < 45% without phlebotomies, and PLT count $\leq 400 \times 10^9/L$, and WBC count < $10 \times 10^9/L$, **and**
 3. No progressive disease, and absence of any haemorrhagic or thrombotic event, **and**
 4. Bone marrow histological remission defined as the presence of age-adjusted normocellularity, and disappearance of tri-linear hyperplasia, and absence of grade > 1 reticulin fibrosis.
- **Partial remission:**
 1. *Durable* resolution of disease-related signs including palpable hepato-splenomegaly, and *large symptoms improvement*, **and**
 2. *Durable* peripheral blood count remission, defined as HCT < 45% without phlebotomies, and PLT count $\leq 400 \times 10^9/L$, and WBC count < $10 \times 10^9/L$, **and**
 3. No progressive disease, and absence of any haemorrhagic or thrombotic event, **and**
 4. No bone marrow histological remission defined as persistence of tri-linear hyperplasia.
- **No response:** any response that does not satisfy partial remission.
- **Progressive Disease:** transformation into post-PV myelofibrosis, myelodysplastic syndrome or acute leukemia (according to the IWG-MRT criteria for the diagnosis of post-PV myelofibrosis and according to WHO criteria for the diagnosis of myelodysplastic syndrome and acute leukemia).

Please note that according to the “new” ELN criteria (i.e. revised ELN response criteria) [2]:

- 1) Molecular response is not required for assignment as Complete Remission or Partial Remission. Molecular response evaluation requires analysis in peripheral blood granulocytes. Complete response is defined as eradication of a pre-existing abnormality. Partial response applies only to patients with at least 20% mutant allele burden at baseline. Partial response is defined as $\geq 50\%$ decrease in allele burden.
- 2) “Durable” is defined as lasting at least 12 weeks.
- 3) “Large symptom improvement” is defined as ≥ 10 points of decrease in MPN-SAF Total Symptom Score [9].

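### Section 22 removes patients who refuse marrow consent from every revised-ELN endpoint, including parameters and non-response classifications that need no marrow result

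*SAP*

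**What the plan says.** SAP section 22 makes marrow histology in Part B subject to a separate consent. Of a patient who declines, it says "this patient can still be recruited in Part B", but then that "this patient will not be counted to assess the related exploratory endpoints". Two endpoints are named: the "overall response rate of Givinostat at the MTD after 6 cycles according to the revised ELN response criteria", and "the evaluation of the effect of Givinostat on each single response parameter according to the revised ELN response criteria". Nothing limits the second to the marrow parameter.

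Section 16.11 builds complete and partial remission from four items joined by 'and'. Items 1 to 3 are the same in substance for both categories:

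- Item 1: durable resolution of disease signs, with large symptom improvement.
- Item 2: durable "peripheral blood count remission, defined as HCT < 45% without phlebotomies", plus platelet and white-cell limits.
- Item 3: no progression and no haemorrhagic or thrombotic event.

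Item 4 is the marrow. For complete remission it reads "Bone marrow histological remission defined as the presence of age-adjusted normocellularity, and disappearance of tri-linear hyperplasia, and absence of grade > 1 reticulin fibrosis". For partial remission it reads "No bone marrow histological remission defined as persistence of tri-linear hyperplasia". No Response is "any response that does not satisfy partial remission".

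Section 19.1 places these same exploratory endpoints on the ITT and PP sets with no condition on marrow consent. Section 5.2 places all efficacy analyses on the ITT set. Section 4 plans the final analysis on 28 patients.

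**The concern.** The exclusion reaches further than the missing result does. A refuser still has haematocrit, platelets, white cells, a symptom score, spleen findings and a record of vascular events. Section 22 nevertheless removes that patient from the revised-ELN summary of each of these. A refuser who clearly fails a blood-count or symptom item is a known non-responder, yet leaves the denominator of the overall rate.

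Three things are at stake:

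- Information is lost from a small sample.
- The rate describes only patients willing to undergo an optional invasive test. If willingness is related to outcome, the rate shifts in a direction nobody can check.
- Sections 5.2 and 19.1 point to one denominator and section 22 to another, so two programmers could produce different tables from the same plan.

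**Working it through.** **Step 1: what the marrow result can change.** The SAP gives no figure on this point to reproduce. I applied the section 16.11 definitions to every combination of three marrow findings (normocellularity, tri-linear hyperplasia, grade >1 reticulin fibrosis), which is 2 × 2 × 2 = 8 patterns.

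| Items 1–3 | Marrow pattern | Patterns | Category as written |
|---|---|---|---|
| At least one not met | any | 8 of 8 | No Response |
| All met | normocellular, hyperplasia gone, no grade >1 fibrosis | 1 of 8 | Complete remission |
| All met | hyperplasia persists, anything else | 4 of 8 | Partial remission |
| All met | hyperplasia gone, but not normocellular and/or grade >1 fibrosis | 3 of 8 | Neither, so No Response |

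The first row shows that a refuser failing any of items 1 to 3 is fully classified without a marrow. The other rows show that for a refuser meeting items 1 to 3 the marrow mostly separates complete from partial remission. In three patterns, read literally, it also decides response against no response. These counts are of patterns, not of expected patients. The literal reading matters because section 16.11 has the exact application of the criteria analysed alongside the investigator's assessment.

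**Step 2: consistency within the SAP.**

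- Sections 5.2 and 19.1 use ITT (and PP) for these endpoints, and Appendix 1 makes the whole analysis population the default denominator. Section 22 removes refusers.
- Section 5.2 counts a patient who stops for a drug-related adverse event before the Cycle 6 assessment as No Response, although nothing was assessed. If that patient had also refused the marrow, section 22 leaves the same patient uncounted.
- Section 22 covers refusal only. Section 5.3.1 lists a consented sample not collected, or a marrow evaluation not done, as minor deviations, with no exclusion stated. The same missing result thus removes a refuser but, as written, not a consenter.

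**Step 3: loss of precision.** The SAP does not give the number of refusers; 4 to 12 of 28 and a 40% rate are assumptions. Half-width = 1.96 × √(0.4 × 0.6 / n).

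| Refusers | n | Half-width |
|---|---|---|
| 0 | 28 | 0.181 |
| 4 | 24 | 0.196 |
| 8 | 20 | 0.215 |
| 12 | 16 | 0.240 |

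**Step 4: how far the rate could move.** Assume 14 of 28 (50.0%) meet items 1 to 3, and count them as responders for the illustration. With r refusers removed, the rate lies between (14 − r)/(28 − r), if every refuser met items 1 to 3, and 14/(28 − r), if none did.

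- r = 3: 11/25 = 44.0% to 14/25 = 56.0%.
- r = 6: 8/22 = 36.4% to 14/22 = 63.6%.
- r = 9: 5/19 = 26.3% to 14/19 = 73.7%.

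These are extremes, not forecasts. If refusers are kept, the uncertainty comes only from those who meet items 1 to 3. Each one adds 1/28 = 3.6 percentage points to the range of the overall rate.

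**The case against.** **Evaluability.** A reader might infer that the marrow serves only to separate complete from partial remission, so that overall response could be judged on items 1 to 3 alone. The SAP does not support that. Persistent hyperplasia is a required item of partial remission, and three of the eight patterns in Step 1 fall to No Response although items 1 to 3 are met. Judging overall response on items 1 to 3 would change the endpoint and could count literal non-responders as responders. Leaving a refuser who meets items 1 to 3 out of the overall rate is therefore a defensible evaluability rule. This stands, but it gives no reason to drop refusers who fail items 1 to 3, or to drop anyone from the non-marrow parameters.

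**Data analysed elsewhere.** It would be too strong to say that the refusers' non-marrow data are lost to the report. Section 19.1 keeps them in each single parameter of the clinico-haematological ELN criteria, in MPN-SAF symptoms and in spleen size. Sections 20.4 and 21 add spleen volume and JAK2 allele burden. What is lost is the revised version of the parameters: 12-week durability, the drop of at least 10 points in total symptom score, and the progression and event item.

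**Low stakes and visible selection.** The primary and secondary efficacy endpoints and the two-stage decision do not use the revised criteria. Section 22 also reports how many patients had a marrow evaluation and lists why others did not. Both points are right and limit the severity.

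**One unclear parameter.** Section 16.11 defines progression by outside diagnostic criteria and does not say which tests they need. If histology were needed, that parameter would be less fully assessed in refusers. Blood counts, symptom score and spleen are unaffected.

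**Conclusion.** The point holds for two groups. All refusers should stay in the non-marrow revised-ELN parameters, because the definitions give no reason to remove them. Refusers who fail any of items 1 to 3 should stay in the overall response as No Response, because their category is already known. For refusers who meet items 1 to 3, the written criteria leave response status open.

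The impact is confined to exploratory, descriptive Part B endpoints. Its size cannot be stated, because the SAP gives no refusal rate. The half-widths rest on an assumed 4 to 12 refusers and a 40% rate; the ranges in Step 4 rest on an assumed 14 of 28. A reader might infer that the reported rate will be biased in a known direction. Nothing in the SAP links marrow consent to response, so it supports only that the rate is exposed to such a selection and that much of the exposure is avoidable. This is a cheap improvement, not a threat to the trial's main conclusions.

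**What to change.** Amend section 22, with a matching line in section 19.1:

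1. Summarise all non-marrow revised-ELN parameters on all ITT patients and, as planned, on PP patients, whatever their marrow consent.
2. In the overall revised-ELN response, count refusers who fail any of items 1 to 3 as No Response.
3. Show refusers who meet items 1 to 3 in their own category, labelled as items 1–3 met, marrow not available. Give the overall rate twice, with this group as responders and as non-responders.
4. Restrict only the complete/partial split and the marrow parameters to patients with a marrow result, and state the number missing.
5. Report the marrow-evaluable subset as a sensitivity analysis.
6. State whether the same handling applies to patients who consented but have no Cycle 6 marrow, since section 22 is silent on them.

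The cost is SAP wording, one extra table category and an overall rate shown as a range instead of a single figure. No new data are needed. Section 3.7 says that, software apart, no analyses change from protocol version 3.0. If the exclusion comes from that protocol, which is not at hand, the departure should also be recorded there.

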23. DOSE MODIFICATION ANALYSIS

For patients who do not tolerate the protocol-specified dosing schedule, dose adjustments are permitted in order to allow the patients to continue the treatment with the study drug.

The objective of the Givinostat dose adjustment rules is to optimize the response for each individual patient, avoiding specific drug-related toxicities. Therefore, dose reductions or interruptions will be mandatory for specific toxicities and dose increases after an initial dose reduction will be allowed in the case of inadequate efficacy at the reduced dosage in absence of specific toxicities.

In the Cycle 1 of **Part A** dose modifications will not be allowed. Patients receiving subsequent cycles of treatment in **Part A** may have up to two dose modifications for drug related DLT's.

Each dose modification has to be recorded on the CRF and the severity of the above mentioned events will be graded according to NCI Common Terminology Criteria for AE (CTCAE v. 4.03, 14th June 2010).

Reason for treatment discontinuation and number of patients treated beyond protocol-specified discontinuation criteria will also be summarised for the safety population.

The following information will be provided for the Dosage Change, by DL (**for Part A only**) and time point:

- Number (n) and percentage (%) of patient with dose temporarily stopped; dose restarted at previous dose; dose restarted and actual dose reduced; dose reduced; dose restarted and actual dose increased;
- Listing of start/end date, type of dose change, single dose (mg) and reason for Change/Interruption.

The calculation of the compliance, in percentage and collapsed in class (Too low, Adequate, Too high), as per [Section 15.1](#) will be capture, for each patient, the deviation from the dose administration plan.

24. OVER-DOSAGE AND OTHER SITUATIONS PUTTING THE PATIENT AT RISK OF ADVERSE REACTION

In general, a drug overdose in a clinical trial is defined as the accidental or intentional use of a drug or medicine in an amount exceeding the protocol defined dose(s). In this Study, if an AE is associated with

Document: PPD

Author: PPD

Version Number:

V2.2

Version Date:

21 March 2018

Template No: CS_TP_BS016 – Revision 3

Reference: CS_WI_BS005

Effective Date: 01May2012

Copyright © 2012 Quintiles Transnational Corp. All rights reserved.

The contents of this document are confidential and proprietary to Quintiles Transnational Corp. Unauthorized use, disclosure or reproduction is strictly prohibited.

(“results from”) the overdose of Givinostat, the AE is reported as an SAE, even if no other criteria for seriousness is met.

If a dose of Givinostat meeting the protocol definition of overdose is taken without any associated clinical symptoms or abnormal laboratory results, the overdose is reported as a non-serious Event of Clinical Interest (ECI), using the terminology “accidental or intentional overdose without adverse effect.” Any instance of overdose (suspected or confirmed, with and without an AE) has to be reported to the Sponsor within 24 hours and, only in case of AEs, it has to be fully documented as a SAE. Details of any signs or symptoms and their management should be recorded in the SAE Form including details of any antidote(s) or systematic treatment administered. Any signs or symptoms of over-dosage are treated symptomatically.

Any other situations putting the patient at risk of adverse reaction, such as misuse and abuse, medication errors, suspect of transmission of infective agents must be reported to the Sponsor within 24 hours and must be fully documented as a SAE.

Listing of patients with overdose reported as a non-serious Even will be provided.

25. PREGNANCY

Female patients who have a positive pregnancy test during the pre-treatment evaluations assessment are not eligible for Study participation. If a patient becomes pregnant while on Study, the treatment is immediately stopped.

Patients are instructed to notify the Investigator if, after completion of the study, it is determined that they became pregnant during the treatment phase or through 3 months after the last dose of study drug.

Whenever possible, a pregnancy with an onset within the above defined time frame is followed until termination, any premature termination is reported, and the status of the mother and child is reported as well after delivery.

If the Investigator is made aware that the partner of a male patient who is participating in the Study become pregnant, he/she is required to report the pregnancy.

Whenever possible, such pregnancy is followed until termination, any premature termination is reported, and the status of the mother and child is reported as well after delivery.

Listing of pregnant patients will be provided.

Document: PPD

Author: PPD

Version Number:

V2.2

Version Date:

21 March 2018

Template No: CS_TP_BS016 – Revision 3

Reference: CS_WI_BS005

Effective Date: 01May2012

Copyright © 2012 Quintiles Transnational Corp. All rights reserved.

The contents of this document are confidential and proprietary to Quintiles Transnational Corp. Unauthorized use, disclosure or reproduction is strictly prohibited.

26. DATA NOT SUMMARISED OR PRESENTED

These variables and/or domains will not be summarised, but they will be listed:

- Comments, with the exception for ECI (if any);
- Investigator signature page*;
- Participation Status* (i.e. Is the patient continuing to the next visit?).

*These variables will not be listed, but will be available in the clinical study database.

Document: PPD

Author: PPD

Version Number:

V2.2

Version Date:

21 March 2018

Template No: CS_TP_BS016 – Revision 3

Reference: CS_WI_BS005

Effective Date: 01May2012

Copyright © 2012 Quintiles Transnational Corp. All rights reserved.

The contents of this document are confidential and proprietary to Quintiles Transnational Corp. Unauthorized use, disclosure or reproduction is strictly prohibited.

APPENDIX 1. PROGRAMMING CONVENTIONS FOR OUTPUTS

DATES & TIMES

Depending on data available, dates and times will take the form respectively

- yyyy-mm-dd or dd-mmm-yyy;
- hh:mm:ss.

SPELLING FORMAT

English UK.

PRESENTATION OF TREATMENT DOSE LEVELS

For MTD analysis set, DLs will be represented as follows and in that order:

Givinostat daily dose	Givinostat dose level (DL)	DL used primarily to asses	Label for Tables, Listings and Figures (TLFs)
100 mg b.i.d.	DL1 (first three patients)	MTD, PK, PD	DL1
	DL1 (additional three patients)		DL1 expanded
2 capsules of 50 mg at the morning AND 1 capsule of 50 mg at the evening (1.e. 12 hours after)	DL6	MTD, PK, PD	DL6
50 mg b.i.d.	DL0	Safety, PK, PD*	DL0

FOR PRESENTATION OF VISITS

Document: PPD

Author: PPD

Version Number:

V2.2

Version Date:

21 March 2018

Template No: CS_TP_BS016 – Revision 3

Reference: CS_WI_BS005

Effective Date: 01May2012

Copyright © 2012 Quintiles Transnational Corp. All rights reserved.

The contents of this document are confidential and proprietary to Quintiles Transnational Corp. Unauthorized use, disclosure or reproduction is strictly prohibited.

For outputs, visits will be represented, if applicable, as follows and in that order:

Study Part	Visit	Visit label for Tables, Listings and Figures (TLFs) ¹
Part A	Screening Visit	A - Baseline
	Cycle 1 Day 1 Visit – PRE-DOSE	A - C1D1 – PRE
	Cycle 1 Day 1 Visit – POST-DOSE	A - C1D1 - POST
	Cycle 1 Day 2 Visit	A - C1D2
	Cycle 1 Day 3 Visit	A - C1D3
	Cycle 1 Day 4 Visit	A - C1D4
	Cycle 1 Day 8 Visit	A - C1D8
	Cycle 1 Day 10 Visit	A - C1D10
	Cycle 1 Day 15 Visit	A - C1D15
	Cycle 1 Day 22 Visit	A - C1D22
	Cycle 1 Day 28 Visit	A - C1D28
	Cycle 2 Day 28 Visit	A - C2D28
	Cycle 3 Day 28 Visit	A - C3D28
	Cycle 4 Day 28 Visit	A - C4D28
	Cycle 5 Day 28 Visit	A - C5D28
	Cycle 6 Day 28 Visit	A - C6D28
	End of Study Visit for completers patients	A – EOS
	Unscheduled Visit n. 1 – PRE-DOSE	A - UNSCHEDULED 1 – PRE*
	Unscheduled Visit n. 2 – PRE-DOSE	A - UNSCHEDULED 1 – PRE*

	Unscheduled Visit n. N – PRE-DOSE	A - UNSCHEDULED N – PRE*
	Unscheduled Visit n. 1 – POST- DOSE	A - UNSCHEDULED 1 – POST*
	Unscheduled Visit n. 2 – POST- DOSE	A - UNSCHEDULED 2 – POST*

Unscheduled Visit n. N – POST-DOSE	A - UNSCHEDULED N – POST*	
Part B	Screening Visit	B - Baseline
	Cycle 1 Day 1 Visit – PRE-DOSE	B - C1D1 – PRE

Document: PPD

Author: PPD

Version Number:

V2.2

Version Date:

21 March 2018

Template No: CS_TP_BS016 – Revision 3

Reference: CS_WI_BS005

Effective Date: 01May2012

Copyright © 2012 Quintiles Transnational Corp. All rights reserved.

The contents of this document are confidential and proprietary to Quintiles Transnational Corp. Unauthorized use, disclosure or reproduction is strictly prohibited.

	Cycle 1 Day 1 Visit – POST-DOSE	B - C1D1 – POST
	Cycle 1 Day 28 Visit	B - C1D28
	Cycle 2 Day 28 Visit	B - C2D28
	Cycle 3 Day 28 Visit	B - C3D28
	Cycle 4 Day 28 Visit	B - C4D28
	Cycle 5 Day 28 Visit	B - C5D28
	Cycle 6 Day 28 Visit	B - C6D28
	End of Study Visit	B - EOS
	Unscheduled Visit n. 1 – PRE-DOSE	B - UNSCHEDULED 1 – PRE*
	Unscheduled Visit n. 2 – PRE-DOSE	B - UNSCHEDULED 1 – PRE*

	Unscheduled Visit n. N – PRE-DOSE	B - UNSCHEDULED N – PRE*
	Unscheduled Visit n. 1 – POST- DOSE	B - UNSCHEDULED 1 – POST*
	Unscheduled Visit n. 2 – POST- DOSE	B - UNSCHEDULED 2 – POST*

	Unscheduled Visit n. N – POST-DOSE	B - UNSCHEDULED N – POST*

1 In all cases, the day of the visit should be reported.* To be ordered on the basis of the date of the visit.

*Drop-out visit refers to patients who prematurely discontinued the treatment showing data recorded during their last assessment visit.

SCREENING FAILURES

Patients who sign an ICF but who do not start Study treatment for any reason, will be considered as “Screening Failures”.

For screening failure patients, a separate Table will be produced including the primary reason for screen failure and patient’s demographic information as per electronic CRF.

LISTINGS

Document: PPD

Author: PPD

Version Number:

V2.2

Version Date:

21 March 2018

Template No: CS_TP_BS016 – Revision 3

Reference: CS_WI_BS005

Effective Date: 01May2012

Copyright © 2012 Quintiles Transnational Corp. All rights reserved.

The contents of this document are confidential and proprietary to Quintiles Transnational Corp. Unauthorized use, disclosure or reproduction is strictly prohibited.

All listings will be ordered by the following:

- Part A
 - DL group;
 - Patient ID;
 - Date (where applicable).

- Part B

Patient ID;

- Date (where applicable).

Document: PPD

Author: PPD

Version Number:

V2.2

Version Date:

21 March 2018

Template No: CS_TP_BS016 – Revision 3

Reference: CS_WI_BS005

Effective Date: 01May2012

Copyright © 2012 Quintiles Transnational Corp. All rights reserved.

The contents of this document are confidential and proprietary to Quintiles Transnational Corp. Unauthorized use, disclosure or reproduction is strictly prohibited.

TEXT CASE

- For titles and column labels, capitalize important words, i.e. nouns, pronouns, verbs, adverbs and adjectives but not articles, conjunctions or prepositions.
- All Footnotes will be in sentence case format.
- All symbols used in body of outputs will be footnoted.
- Continuous Variables:
 - Number (“n”),
 - Mean,
 - Standard Deviation (“SD”),
 - Median,
 - Minimum (“min”),
 - Maximum (“max”)

will be presented for all variables on the original scale.

- Categorical Variables:
 - Number (“n”),
 - Percentage (%)

in each category will be the default summary presentation.

- The percentage of patients in each category relative to the total number of patients in the relevant analysis population will be the default. Percentages relative to the total number of patients in the relevant analysis population with a non-missing assessment will be specified in a programming note on the shell if required.
- Where percentages are presented, a footnote will be added to explain what the denominator of the percentage is, in the form “Percentages are calculated relative to the total number of patients in the SAF” as the first footnote.
- All computed percentages will be presented using one decimal place except for where the percentage is 100 where no decimal places are presented.
- The percentage will be also presented if the count is zero.

Document: PPD

Author: PPD

Version Number:

V2.2

Version Date:

21 March 2018

Template No: CS_TP_BS016 – Revision 3

Reference: CS_WI_BS005

Effective Date: 01May2012

Copyright © 2012 Quintiles Transnational Corp. All rights reserved.

The contents of this document are confidential and proprietary to Quintiles Transnational Corp. Unauthorized use, disclosure or reproduction is strictly prohibited.

